## **8.12 Volunteer Termination and Withdrawal**

Situations that may cause an early termination or withdrawal of a volunteer from the study are described below.

### **8.12.1 Reasons for Termination**

#### **8.12.1.1 Self-Withdrawal Criteria**

Volunteers are always free to withdraw themselves from the study at any time without prejudice or penalty. They are not required to disclose a reason for their decision. Volunteers who withdraw themselves from the study are compensated as indicated in section 10.6 "Financial Incentives to Volunteers."

#### **8.12.1.2 Other Termination Criteria**

In rare circumstances, a volunteer's participation may be terminated without his/her consent if unplanned conditions occur (e.g., website failure). In these cases, volunteers will be compensated as indicated in Section 10.6, "Financial Incentives to Volunteers."

### 8.12.2 Termination and Withdrawal Procedures

Individuals may withdraw by simply navigating away from the study webpage without completion or not returning for the second time point. These withdrawals will not be considered to be associated with a UPIRTSO and/or significant and adverse reaction and therefore not reported to HSPB. Volunteers are not required to contact a research team member before they withdraw. However, if the research team discovers evidence of a withdrawal associated with a UPIRTSO or significant and adverse reaction to the study, (e.g., if a volunteers chooses to contact the PI or other team member about their withdrawal and it appears to be associated with a UPIRTSO and/or significant and adverse reaction to the study) this will be promptly reported to the WRAIR IRB within 48 hours [via e-mail to the HSPB electronic mailbox ([[contact]](mailto:[contact])) and the HSPB Point of Contact (POC)].

### 8.13 Quality Control and Assurance

All applicable MPB and ARL standard operating procedures will be followed.

## 9 STATISTICAL METHODS AND DATA ANALYSIS

### 9.1 Analyses for Main Study Hypotheses

Between group differences (comparing real vs. fake HBMT) in the change in state anger and state HAB across time points (change from time-point one to time-point two) will be primarily assessed with a mixed-designs ANOVA. Between group differences in state aggression measured at time-point two will be assessed with a General Linear Models (GLM) analysis controlling for trait anger and demographics (age and gender).

We will also plot effect of group comparing real vs. fake HBMT and time between time-points (24-96 hours) on change scores (time 2 anger/aggression minus time 1 anger aggression) and analyze this using a linear regression with an interaction term.

Lower order effects will be tested using corrected Fishers LSD, Tukey, Scheffe, or other pairwise test as appropriate. Appropriate data-transformations may be used as necessary to satisfy significance test requirements. Lower order effects will also be assessed with pairwise dependent means t-tests. Age and gender will be controlled as covariates. Mediation analyses (if used) will be performed using non-parametric Monte-Carlo bootstrapping procedures using PROCESS (see Hayes, 2017).

We may use age, gender, and trait measures as control variables in analyses.

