The study would utilize up to 400 volunteers (200 completers) recruited via an online commercial recruitment platform to participate in an online study. Volunteers will be asked to participate at two time-points. At time-point one, volunteers would be randomly assigned to complete one of two versions of HBMT. One version is designed to train the brain (rehearse and reinforce) to seek positive interpretations of ambiguous social cues and to inhibit thoughts and behaviors related to hostility. The second is a placebo version that is not expected to affect attitudes, cognitions, or behaviors. These versions were validated in a prior study (WRAIR #2574). Volunteers will also complete some brief surveys to assess state emotion, trait anger, and HAB. Volunteers will be asked to return between 24 and 96 hours later to complete another brief measure of HAB, state emotion, and a brief self-report survey about their online (public behavior only), driving, and other behaviors over the preceding 24 hours. We hypothesize that volunteers who receive the genuine training will display the less hostile bias and report lower anger and aggression in their daily behaviors when assessed at the second time-point.

If successful, these findings would provide evidence that HBMT is effective in affecting real-life behaviors and help convince potential stakeholders of the value of HBMT. Future research could validate effectiveness in operational units as well as with unhealthy populations (e.g., anger management groups). Future research could also test the effectiveness of HBMT on behavioral health outcomes for usage by clinicians and portable use by individuals with unhealthy hostile bias and problems with social aggression when isolated from traditional behavioral health care (e.g., far forward deployed units).

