### **3.4 Efficacy Data Collected**

Main endpoints for the study include: self-report measures of HAB and self-report measures of daily aggressive behaviors.

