## **5 HYPOTHESES**

### **5.1 Primary Hypotheses**

- a. Hypothesis 1: Relative to volunteers in the fake-training condition, those volunteers who receive the real HBMT at time-point one will report less state anger and aggression at time-point two.
- b. Hypothesis 2: Effects of HBMT on state anger and aggression in daily life will be mediated by between group differences in HAB.

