### 7.2 Determination of Sample Size

200 volunteers (100 completers per condition) are needed to achieve statistical power of 80% and equal groups. The previous (and only other) study to test HBMT found a large effect of the real (vs. placebo) training on HAB ( $d = .78$ ), when HAB was assessed immediately after HBMT. However effect sizes are expected to be smaller in the present study as actual behavior is being assessed and there is a greater time delay (24-96 hours) between HBMT and the behavioral assessment. We will divide this effect size approximately in half ( $d = .4$ ) in our prediction for the second study. Given this effect size, a minimum of 200 completers who follow all task instructions will be needed to achieve 80% power.

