### 8.8 Study Procedure

The procedural flow of the experiment with estimated times for each step is outlined below. The study will not proceed until/unless the volunteer clicks that they have read the ICD and agree. The times provided are only estimates of the duration we anticipate the typical volunteer will use.

Time-point One:

- a. Volunteer arrives at study webpage and reviews ICD (estimated to take approximately 1-2 minutes)
- b. Volunteer completes trait anger questionnaire (1 minute)
- c. Volunteer Completed State Emotion Questionnaire (3 minutes)
- d. Volunteer reads instructions for real/fake HBMT (1 minute)
- e. Volunteer completes real/fake HBMT (15 minutes)
- f. Volunteer completes ACS Scale (set A) (10 minutes)
- g. Volunteer completes demographic items (< 1 minute)
- h. Volunteer is thanked for participation (< 1 minute)

Time-Point Two (24-96 hours later)-volunteers will received daily reminder e-mails via anonymous mturk.com functionality during interim.

- i. Volunteer arrives at study webpage and reviews ICD (same ICD as from time 1; estimated to take approximately 1-2 minutes).
- j. Volunteer Completes ACS (set B) (10 Minutes)
- k. Volunteer Completed State Emotion Questionnaire (3 minutes)
- l. Volunteer Completes State Measure of Aggression (10 Minutes)
- m. Volunteer is thanked for participation (< 1 minute)

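### The planned HAB test compares two post-training scores, so it measures whether the effect lasts or fades, not whether training lowered HAB

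*Combined protocol and SAP*

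**What the plan says.** Section 9.1 states that "Between group differences (comparing real vs. fake HBMT) in the change in state anger and state HAB across time points", from time-point one to time-point two, are to be assessed primarily by a mixed-design ANOVA. A between-group difference in change is the group-by-time term of that model.

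Section 8.8 gives the order of events at time-point one. Trait anger and state emotion come first (steps b and c). Then "Volunteer completes real/fake HBMT (15 minutes" minutes (step e), and after it "Volunteer completes ACS Scale (set A) (10 minutes" minutes (step f). ACS set B follows at time-point two (step j). No ACS is given before training.

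The standing of HAB is set out elsewhere:

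- Section 3.4: "Main endpoints for the study include: self-report measures of HAB", listed together with daily aggressive behaviour.
- Précis: volunteers given the genuine training "will display the less hostile bias and report lower anger and aggression in their daily behaviors when assessed at the second time-point".
- Section 5.1, Hypothesis 2: effects on anger and aggression "will be mediated by between group differences in HAB".

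Appendix B divides the ACS into six subscales. Its only scoring rule is to sum the 1–5 responses within each.

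**The concern.** A change score measures a treatment effect when the first score is taken before treatment. That holds for state anger (step c). It does not hold for HAB, where both scores follow randomised training. If training lowers HAB by the same amount at both time-points, the two arms change equally and the interaction is zero. If the benefit fades, HAB rises more in the real-training arm, and the interaction looks like harm.

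Fading is a realistic prospect. The earlier study's d = .78 was obtained "when HAB was assessed immediately after HBMT", which is where set A sits here, and Section 5.2 expects the effects on anger and aggression to diminish with time. A training that works could thus be reported as failing, or as reversed, on a listed main endpoint.

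The two ACS sets also differ in length. Summed without rescaling, they put the two time-points on different ranges, which distorts the change score in its own way.

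**Working it through.** **The plan's own figure.** Section 7.2 asks for 100 completers per arm for 80% power at d = .4. A two-sided, two-group comparison of a single score at .05 needs 99 per arm, and 100 per arm gives 80.4% by the noncentral t. So the stated size corresponds to comparing the arms on one score.

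**Inputs.** From Section 7.2: d1 = .78 just after training and n = 100 per arm. From Section 9.2: α = .05, taken two-sided. Assumed, because the documents do not give them: the HAB effect at time-point two, d2 = .4 to .78, and the correlation between time-points, r = .3, .5, .7. The plan's .4 is a planning value for delayed behaviour, since "effect sizes are expected to be smaller in the present study as actual behavior is being assessed"; it is not an estimate for HAB.

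**Common scale (SD 1 at each time-point).** With d as the reduction in HAB:

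- Difference in change, real minus fake = d1 − d2, and SD of change = √(2(1 − r)).
- Standardised interaction = (d1 − d2)/√(2(1 − r)), tested on 198 df with noncentrality equal to that value × √(100/2).
- Example, d2 = .4 and r = .5: .38/1 = .38; .38 × 7.07 = 2.69; probability of significance in the wrong direction .762.

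| d2 | Wrong direction, r = .3 / .5 / .7 | Benefit direction | Direct time-two test |
|---|---|---|---|
| .4 | 62 / 76 / 93% | about 0% | 80% |
| .6 | 19 / 24 / 37% | about 0.1% or less | 99% |
| .7 | 7 / 8 / 11% | 0.7 / 0.6 / 0.4% | over 99% |
| .78 | 2.5% | 2.5% | over 99% |

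The group main effect of the same ANOVA, ((d1 + d2)/2)/√((1 + r)/2), has power of at least 99.4% in every row.

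**Raw sums.** In the Appendix B scoring table, every subscale has 4 items numbered 1–24 (set A) and 5 numbered 25–54 (set B). The ranges are 4–20 and 5–25. At an unchanged item mean of 2.5, the sum moves from 4 × 2.5 = 10 to 5 × 2.5 = 12.5 in both arms. A constant per-item group difference m becomes 4m and then 5m, which is 25% larger at time-point two.

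Take item SD 1 and an assumed inter-item correlation ρ = .2 to .6. The SD of a k-item sum is SDk = √(k + k(k − 1)ρ). The contrast is d1·SD4 − d2·SD5, and the SD of change is √(SD4² + SD5² − 2r·SD4·SD5). Example, ρ = .4, r = .5, d2 = .4: SD4 = 2.966 and SD5 = 3.606; contrast 2.313 − 1.442 = .871; SD of change 3.332; ratio about .26; wrong-direction probability about 45%. Across ρ:

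- d2 = .4: wrong direction 33–38%, 43–50% and 62–70% for r = .3, .5, .7.
- d2 = .6: wrong direction 4–8%.
- Constant per-item effect (contrast 4m − 5m, with 4m = .78·SD4): significant apparent benefit in about 18%, 23% and 34–36%.

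So sums partly mask a reversal, and they can make an effect that merely lasts look as if it grows.

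**The case against.** The strongest reply is that the planned model already contains a valid answer. With two randomised post-training scores, the ANOVA's group main effect tests whether training lowered HAB, and with very high power. Section 9.1 also provides for lower-order tests. This is correct, and it means the data can answer the question. But 9.1 names change as what is primarily assessed, leaves the choice of pairwise procedure open, and specifies dependent-means t-tests, which compare time-points within a person and not the arms. Which result counts as the HAB finding would be decided after the results are seen.

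Second, HAB as mechanism is only a secondary objective (Section 4.2), and Hypothesis 1 concerns anger and aggression. The documents are mixed here: Section 3.4 lists HAB among the main endpoints, and the mediation hypothesis stands under the primary hypotheses. The tests of Hypothesis 1 are untouched. Nor does 9.1 say that a mediation analysis would use the change score, so the fault does not automatically carry into Hypothesis 2.

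Third, the largest probabilities need a time-two HAB effect of .4 on a common scale. That is fair: over the ranges examined, the wrong-direction risk runs from 2.5% to 93%. The structural point needs none of these inputs.

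Fourth, Section 3.3 gives no sequence within time-point one, and the Appendix A advertisement mentions the scenarios before the vocabulary task. Neither sets an order; Section 8.8 is the only step-by-step procedure. Were the ACS given before training, the objection would fall away.

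Finally, the plan does not say which ACS subscale or total is the HAB score. That gap stands, and rescaling alone does not close it.

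**Conclusion.** The concern holds for HAB and must be fixed. The contrast named as primary estimates persistence or decay and does not match the Précis prediction of a lower level at time-point two. With 100 per arm and a common scale, it has at most a 2.5% chance of showing a significant HAB benefit for time-two effects of .4 to .78 after an immediate effect of .78. The direct comparison has 80% to over 99% power across the same range. The chance of a significant reversal is 62–93% if the effect falls to .4, and 2.5% if it is fully sustained.

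These figures rest on assumed correlations and an assumed time-two HAB effect. That a lasting effect has an expected interaction of zero on a common scale rests only on the order of measurement in Section 8.8. The unequal ACS forms are a separate scoring fault, confirmed from Appendix B.

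**What to change.** In Section 9.1:

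- Keep the mixed ANOVA for state anger and take HAB out of it.
- Name the between-group comparison of set B at time-point two as the HAB efficacy test. Report set A at time-point one as the immediate effect. Adjust both for covariates already collected that are fixed or precede training: trait anger, time-one state anger, age and gender.
- Score both sets as item means, and state which subscale or total is the HAB score.
- If the group-by-time term for HAB is retained, label it a test of decay, not of efficacy.
- If mediation is run, use set A as the mediator. It precedes the 24-hour recall period of the aggression questionnaire (Appendix F), whereas set B is completed after it.

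The cost is wording in the analysis section and a scoring line. Procedure, data collected and number of volunteers stay the same.

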### **5.2 Secondary Hypothesis**

- a. The effects of HBMT on anger and aggression will diminish over time. In other words, larger effects of HBMT will be observed for volunteers returning sooner (vs later) after time-point one.
- b. We anticipate the most robust impact of HBMT on anger and aggression on high versus low stress days (per self-report).

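### State anger is tested by change from time 1 to time 2; adjusting for the pre-training anger score would use the same volunteers with about (1+r)/2 of the variance

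*Combined protocol and SAP*

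**What the plan says.** Hypothesis 1 (Section 5.1) is that "those volunteers who receive the real HBMT at time-point one will report less state anger and aggression at time-point two". State anger is thus one of its two outcomes.

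For state anger and HAB, Section 9.1 compares the arms on the "change from time-point one to time-point two) will be primarily assessed with a mixed-designs ANOVA". The next paragraph of 9.1 examines arm and time between visits "on change scores (time 2 anger/aggression minus time 1 anger aggression) and analyze this using a linear regression with an interaction term". That serves the Section 5.2 hypothesis that "The effects of HBMT on anger and aggression will diminish over time".

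On covariates, 9.1 says "Age and gender will be controlled as covariates" and allows trait measures as optional controls. Time-1 state anger is not named. ANCOVA appears in the abbreviation list but in no analysis.

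Section 8.8 gives the order of measurement:

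- Time-point one, before the training instructions (step d) and the training (step e): "c. Volunteer Completed State Emotion Questionnaire (3 minutes".
- Time-point two, same instrument: "k. Volunteer Completed State Emotion Questionnaire (3 minutes".
- Time-point one, after the training: "f. Volunteer completes ACS Scale (set A) (10 minutes". This is the HAB measure.
- The State Aggression Questionnaire is listed at time-point two only.

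**The concern.** Subtracting the time-1 score fixes its coefficient at 1. ANCOVA estimates that coefficient from the data. Unless the true slope is 1, subtraction puts time-1 noise into the outcome, and the noise is greatest when the two scores are weakly correlated. State emotion over two different 24-hour windows may well be only moderately correlated.

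The time-1 anger score is a genuine pre-treatment measurement, and everyone with a change score has it. The plan therefore gives up precision on one of the two Hypothesis 1 outcomes, and again on the anger part of the decay analysis, without gaining anything in return. Precision per completer matters here because Section 3.2 expects up to 50% drop-out.

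**Working it through.** **The plan's own figure.** Section 7.2 gives d = .4, 80% power and 100 completers per arm. By the normal approximation, n per arm = 2(1.96 + 0.8416)²/0.4² = 98.1, so 99 per arm or 198 in all, which agrees with 200. Noncentral t power at 100 per arm is 80.4%. A one-sided calculation needs only 78 per arm, so the 200 rests on a two-sided two-sample comparison with no baseline term. Section 7.2 does not say whether d is on the time-2 SD or the change-score SD.

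**Equivalence.** With two groups and two times, the group-by-time test in the mixed ANOVA is the two-sample test on change scores (a regression of change on arm, age and gender once those are added).

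**Variances.** With a common SD s and correlation r:

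- change: 2s²(1 − r)
- ANCOVA: s²(1 − r²)
- ratio, ANCOVA to change: (1 − r²)/[2(1 − r)] = (1 + r)/2

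At r = .3, .5, .7 the ratio is .65, .75, .85. Inverted, the change test has 1/.65 = 1.54 times the ANCOVA variance at r = .3 and 1/.75 = 1.33 times at r = .5. Simulation (100 per arm, 4,000 runs per setting) gave .65–.67, .75–.76 and .83–.86, with both methods estimating about −.40.

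**Worked case: r = .3, d = .4 on the time-2 SD.**

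- Change: SD = √1.4 = 1.183; .4/1.183 = .338; noncentrality .338 × √50 = 2.39; power 66%.
- ANCOVA: SD = √.91 = .954; .4/.954 = .419; noncentrality .419 × √50 = 2.96; power 84%.

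**Power over an assumed range of r.** 100 per arm; age and gender in both models and assumed uninformative; chance covariate imbalance averaged over. Each cell is change / ANCOVA.

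| r | time-2 SD, two-sided | time-2 SD, one-tailed | change SD, two-sided |
|---|---|---|---|
| .2 | 60% / 81% | 72% / 89% | 80% / 95% |
| .3 | 66% / 83% | 77% / 90% | 80% / 93% |
| .4 | 72% / 86% | 82% / 92% | 80% / 92% |
| .5 | 80% / 90% | 88% / 94% | 80% / 90% |
| .7 | 95% / 97% | 98% / 99% | 80% / 86% |

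Direct simulation (10,000 runs, time-2 SD, two-sided) gave .657/.798/.952 against .835/.898/.975 at r = .3/.5/.7. Type I error was 4.6–5.3% for change and 4.8–5.1% for ANCOVA.

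**Unequal SDs.** Let k = SD1/SD2. In time-2 SD units the change variance is 1 + k² − 2kr and the ANCOVA variance is 1 − r². The difference is (k − r)², which is never negative. At r = .3/.5/.7 the ANCOVA-to-change ratio is .78/.89/.98 for k = .8 and .50/.57/.63 for k = 1.25.

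**Price of the covariate.** Chance imbalance on time-1 anger raises the arm-effect variance by about 0.5%. With equal SDs, ANCOVA loses only if r exceeds 2/1.0052 − 1 = .99.

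**Does optional trait anger recover the loss?** No. In simulation with trait anger equally correlated with both scores, adding it left the change-score variance at 1.00–1.01 of its unadjusted value.

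**Regression on hours since training.** For the arm-by-hours term, the simulated variance ratio was .65, .75 and .85 at r = .3, .5 and .7. In one assumed scenario (effect falling linearly from .8 SD at 24 h to 0 at 96 h, uniform return times), two-sided power was 28% against 40%, 35% against 46%, and 54% against 61%.

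**The case against.** **No error is shown.** The change test is valid. On the change-SD reading it has the stated 80% at every r. Only the time-2-SD reading with r below about .5 falls short two-sided, and one-tailed testing under Section 9.2 removes most of that (82% at r = .4). This stands: the point concerns efficiency.

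**The size is uncertain.** r is unknown, and (1+r)/2 needs equal SDs. With SD1/SD2 = .8 the saving is 11% at r = .5 and 2% at r = .7; with k = r it is nil. This also stands for the size. The direction does not depend on it, because (k − r)² cannot be negative. Nor does it need normal scores: simulated five-point, floor-skewed scores gave ratios of .54, .61 and .68 at r = .3, .5 and .7.

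**The two methods agree only if the analysed arms are comparable.** The analysed set is completers, and the 60%-correct rule in Section 3.2 applies to different tasks in the two arms. If completers differ by δ SD at time 1, the estimates differ by (1 − r)δ, for example .5 × .2 = .10 SD. This is a fair caution, but it does not favour change scores. When drop-out depends on arm and time-1 anger, ANCOVA conditions on the variable driving selection. In a simulation of that kind with true effect −.40, ANCOVA gave −.40 and change gave −.29.

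**Lesser points.** Section 3.4 lists HAB and aggressive behaviour, not anger, as main endpoints; but 3.1, 4.1 and 5.1 make anger primary. Dropping the mixed ANOVA for anger does not strand the dependent-means t-tests in 9.1, which need no parent model. The decay scenario is illustrative only.

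**Conclusion.** The point holds, for state anger only. The planned analysis is valid but less precise than an ANCOVA on a pre-training score already collected. With equal SDs the saving in variance is 35%, 25% and 15% at r = .3, .5 and .7. The exact size rests on an r and an SD ratio that the documents do not give; the direction rests on neither, apart from a finite-sample cost of about 0.5%. Describing this as lost precision and not bias assumes that randomisation still balances the analysed completers. No shortfall against the 80% in Section 7.2 is established. The change is worth making because it costs almost nothing and also fits Hypothesis 1, which is worded as anger at time-point two.

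**What to change.** Make two changes in Section 9.1, both for state anger only.

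1. Replace the mixed ANOVA with: *State anger at time-point two will be compared between arms by ANCOVA with time-point-one (pre-HBMT) state anger as covariate, together with age and gender; this is the primary test of Hypothesis 1 for state anger.*
2. In the regression on time between visits, replace the anger change score with: *State anger at time-point two will be regressed on arm, hours between time-points and their interaction, with time-point-one state anger as covariate.*

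Do not treat time-1 HAB this way: it is measured after training, so adjusting for it would adjust for a post-treatment variable. Leave the aggression GLM and Sections 7.2 and 9.2 as they are.

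The cost is wording. No new data are needed and the same volunteers are analysed. Adding time-1 anger costs about 0.2 points of power if it is uninformative. All three covariates together cost up to about 0.6 points (80.4% to 79.8% at r = 0), and age and gender are already planned.

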#### 3.3 Study Design, Methodology, and Experimental Manipulations

The study consists of a two group design. Assignment to each of the two experimental conditions is determined randomly upon the volunteers’ arrival to the study webpage. However, the website will be programmed to achieve equal sample size across the two groups. The duration of participation for each volunteer is estimated to be about 60 minutes (total, including both time-points). Volunteers will complete the following as part of the study:

- a. HBMT: Volunteers will complete a computer-based hostile bias modification training where they are instructed to complete word fragments (words with missing letters) to form non-aggressive words. The word fragments are based on similar stimuli used in prior research on hostile bias (Anderson, Carnagey, & Eubanks, 2003; DeWall & Bushman, 2009). This task was validated in a previous study (WRAIR # 2574).
- b. Angry Cognitions Scale/HAB measure: This measure asks respondents to read hypothetical scenarios and indicate how they would interpret and respond to them. It was developed by Martin and Dahlen (2007) and will be used as a measure of HAB.
- c. Trait anger Scale: Brief measure of trait anger validated by Wilk et al., (2015).
- d. State Aggression Survey: This survey is adapted from several others in the literature to measure variance along the normal spectrum of aggressive behaviors in daily life that the average person might display (Álvarez-García, et al., 2016; Deffenbacher, et al., 2001; Deffenbacher, J. et al., 2002). The survey specifically asks about driving behaviors (e.g., yelling at other drivers), and public online behaviors (e.g., posting mean comments on social media), as well as generic public displays of aggression items (e.g., Gotten angry and slammed a door).

- e. State Emotion Survey: A short measure of state (current or recent) emotions over the preceding 24 hour period adapted from Goldberg et al., (2006) and Quartana and Burns (2007).
- f. Demographic questions: Volunteers will be asked to provide their age (whole number, not birth date), highest level of education, and gender. These will be used as statistical controls in analyses.

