**I am a hotheaded person.**

1 = Strongly Disagree	2	3	4	5 = Strongly Agree
--------------------------	---	---	---	-----------------------

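### The time-point-two aggression model leaves out pre-training state anger, which is already collected: a missed gain in precision of uncertain size, not a bias

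*Combined protocol and SAP*

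**What the plan says.** Section 9.1 plans a General Linear Model for between-group differences in state aggression at time-point two. The outcome "will be assessed with a General Linear Models (GLM) analysis controlling for trait anger and demographics (age and gender"). The trait anger form (Appendix G) has two items; the first is "I am a hotheaded person".

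Section 8.8 gives the order of events:

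- Time-point one, step c: "Volunteer Completed State Emotion Questionnaire (3 minutes"). This comes before the training instructions (step d).
- Time-point one, step e: "Volunteer completes real/fake HBMT (15 minutes").
- Time-point one, step f: "Volunteer completes ACS Scale (set A) (10 minutes"). This comes after training.
- Time-point two, step l: "Volunteer Completes State Measure of Aggression (10 Minutes"). The aggression form appears nowhere at time-point one.

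On covariates in general, Section 9.1 closes with "We may use age, gender, and trait measures as control variables in analyses". Section 3.3f, after listing age, education and gender, says "These will be used as statistical controls in analyses". The time-point-one state emotion data are used in 9.1 for the change in state anger. No sentence brings them into the aggression model.

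**The concern.** Aggression in daily life is part of the primary objective (4.1a) and of Hypothesis 1 (5.1a). With no pre-training aggression score, the model must rely on other baseline measures to remove between-person variation. The one anger measure it uses is a two-item trait score.

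The State Emotion Questionnaire (Appendix H) asks about the past 24 hours, the same length of recall as the aggression form (Appendix F), and includes items on feeling angry, being easily irritated and not being easily annoyed. Assignment may take place on arrival at the webpage (3.3, 8.5), but nothing that differs between arms happens before step d, so the step c answers are valid baseline data. The Angry Cognitions Scale set A cannot play this part because it follows training.

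At stake is precision on an outcome for which 7.2 plans 80% power at a halved effect size, in a study that expects up to 50% drop-out (3.2). Extra completers are costly there; a measure already in hand is not.

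**Working it through.** **Inputs.** d = 0.4, 100 completers per arm and 80% power (7.2); alpha 0.05, one-tailed for the directional hypotheses of 5.1 (9.2). The partial correlation r of pre-training state anger with time-point-two aggression, given trait anger, age and gender, is not in the documents. It is an assumption, shown from 0.1 to 0.5.

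**Step 1: the plan's own figure.** A two-sided two-sample t-test at d = 0.4 needs 99.08 per arm, rounded up to 100, so 200 in total. Power at 100 per arm is 80.4%. The stated 200 is therefore reproduced, as a two-sided calculation without covariates. A one-tailed calculation needs 78 per arm (156). At 100 per arm, one-tailed power is 88.0%.

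**Step 2: effect of adding the covariate.** The residual SD is multiplied by √(1 − r²), and so is the standard error. Power comes from the noncentral t distribution with 198 degrees of freedom and noncentrality 0.4 × √(100/2) / √(1 − r²), which is 2.83 at r = 0. The equivalent number of completers is 200/(1 − r²). This table assumes that trait anger, age and gender explain nothing.

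| Assumed r | Fall in standard error | One-tailed power | Two-sided power | Equivalent completers |
|---|---|---|---|---|
| 0 | 0 | 88.0% | 80.4% | 200 |
| 0.1 | 0.5% | 88.3% | 80.8% | 202 |
| 0.2 | 2.0% | 89.1% | 81.9% | 208 |
| 0.3 | 4.6% | 90.5% | 83.9% | 220 |
| 0.4 | 8.3% | 92.4% | 86.7% | 238 |
| 0.5 | 13.4% | 94.6% | 90.1% | 267 |

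The one-tailed column is the one that matches 9.2.

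**Step 3: a starting point with the existing covariates.** Suppose these explain a share R² of the variance (also an assumption). The residual SD becomes √[(1 − R²)(1 − r²)].

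- R² = 0.10: one-tailed power starts at 90.8% and becomes 91.7% at r = 0.2, 92.9% at r = 0.3 and 96.3% at r = 0.5.
- R² = 0.20: it starts at 93.4% and becomes 94.2%, 95.1% and 97.7%.

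The percentage fall in the standard error from adding the covariate is the same as in the table, but the gain in power is smaller.

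**Step 4: what r could be after trait anger.** With correlations a (state anger with aggression), b (trait anger with aggression) and c (state with trait), r = (a − bc)/√[(1 − b²)(1 − c²)]. Two assumed cases, ignoring age and gender:

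- a = 0.3, b = 0.4, c = 0.5: r = 0.10/√(0.84 × 0.75) = 0.126, and the standard error falls by 0.8%.
- a = 0.5, b = 0.3, c = 0.5: r = 0.35/√(0.91 × 0.75) = 0.424, and the standard error falls by 9.4%.

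So a negligible gain and a useful gain are both compatible with what the documents say.

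**The case against.** The strongest reply is that this is a preference about efficiency. The model already adjusts for a pre-training anger measure, the arms are randomised, and no passage is contradicted by the omission. The time-point-one state data are not wasted, since they serve the state anger analysis. Time-point two is at least 24 hours after time-point one, so the two 24-hour recall windows do not overlap, and nothing in the documents shows that state anger predicts aggression beyond trait anger. All of this stands. It limits the size of the point but does not remove it: the expected gain is positive for any non-zero r.

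It also stands that the covariate is not entirely free. Volunteers may skip survey questions without losing payment (10.6), missing data are not imputed, and cases are dropped pairwise or listwise (9.4). If the new covariate cost 5 volunteers per arm (an assumption), one-tailed power at r = 0.2 would be 87.7%, slightly below the 88.0% without it. The missing-item rule is therefore a necessary part of the fix.

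A reader might infer that the rise from 80.4% to 90.1% measures the loss. It does not: those figures are two-sided, start from a model with no covariates, and take the top of an assumed range.

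A reader might also infer that the aggression covariates can be chosen once results are known. The documents do not go that far. The aggression sentence in 9.1 itself commits to trait anger, age and gender, and 9.5 requires departures from the plan to be described and justified. What remains is a real but secondary inconsistency: 3.3f makes education a control, 9.1 does not, and the closing sentence of 9.1 turns firm covariates into optional ones.

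**Conclusion.** The point holds as a missed gain in precision. Pre-training state anger is collected before any difference between arms, aggression has no baseline, and the aggression model does not use the measure.

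The standard error would fall by about 0.5% to 13% for r between 0.1 and 0.5. One-tailed power would rise from 88.0% to between 88.3% and 94.6% if the existing covariates explain nothing, with smaller gains otherwise. If r is 0.3 or less, the gain is at most about 2.5 percentage points (90.5 − 88.0). These sizes rest on assumed values of r and on d = 0.4 being the standardised effect before adjustment.

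Two stronger readings are not supported. The omission does not bias the randomised comparison. Nor does it make the 200 completers wrong, because that number is reproduced without counting on any covariate gain.

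**What to change.** In 9.1, state one aggression model: group, pre-training state anger, trait anger, age and gender. Define pre-training state anger as the mean of the available time-point-one items on feeling angry, being easily irritated and (reverse-scored) not being easily annoyed. Appendix H gives no scoring rule, so this definition has to be written down before the data are analysed.

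Keep volunteers who skipped some or all of these items. Use the mean of the items answered and, if none was answered, the overall baseline mean calculated without regard to group. Section 9.4 rules out imputation, so it needs a stated exception for this covariate. It should also say that the missing-data and outlier exclusions do not drop a volunteer on account of this score.

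Delete the sentence "We may use age, gender, and trait measures as control variables in analyses" and make 3.3f agree with the list in 9.1, including on education. Do not use the Angry Cognitions Scale set A as a baseline, because it follows training.

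The cost is wording, one degree of freedom and the short rule for missing covariate items. No new data are needed.
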